#### II. Summary of Procedures

All proposed studies will be conducted at Children's Healthcare of Atlanta (Atlanta, GA) for a total duration of 24 months. Local institution review board approval would be obtained prior to the study. The table below (Table 1) provides an overview of the timeline and specific tasks to be completed upon each visit. Baseline represents the initial visit after the patient has been screened and meets the inclusion criteria (EKG results may take 24-48 hrs and study participant will be advised to start the study intervention once confirmation of normal EKG is obtained) Patients will be scheduled to visit the clinic for follow up visits at the pre-set time points shown. A total of 15 subjects, from age 5 years to 21 years, will be included in the study. The stimulation devices used in this study are VitalStim 400, electrical neuromuscular stimulators, which have been used in multiple previous clinical studies for modulation of pain and have received FDA approval. The (2) electrodes for the device will be placed on the subjects left cervical (neck) region. The stimulator will be placed in a comfortable position, such as next to the pillow. The stimulators are battery-powered and allow configuration of the stimulation parameters to the comfort of the patient. Parents will be trained on where to place electrodes, how to ensure that the electrodes make a good contact with the skin, and how to set the stimulation parameters.

#### SCHEDULE of Events

STUDY PROCEDURES (*experimental procedure)	Baseline	3 mon	6 mon	9 mon	12 mon	15 mon	18 mon	21 mon	24 mon
Informed consent	x								
Inclusion/exclusion criteria	Х								
Medical history	Х	х	х	х	х	х	х	х	х
*nVNS 2 times daily x 60 mins each (log book maintained and reviewed)	x	x	x	x	x	x	x	x	x
Physical and neurological examination	x		х		х		х		х
Vital Signs	Х		х		х		х		х
Cytokine profile	Х		х		х		х		х
EKG	Х		х		х		х		х
R-ODS scale and handheld dynamometer	х		х		х		х		х
Nerve conduction study	x				х				х
Adverse events	х	х	х	х	х	х	х	х	х
Concomitant medications (IVIG, steroids, PLEX)	х	х	х	х	х	х	х	х	х
Telephone visit/ check (To limit inperson visits due to COVID-19 pandemic)		х		х		х		x	

**Table 1. Study outline for nVNS in CIDP patients.** Patients will be followed for two years with nVNS as an adjunctive to standard IVIG therapy. Patients will be validated against the stated inclusion criteria prior to enrollment in the study. Baseline measurements before nVNS is added will be taken to determine change in physiological and functional outcomes over time. All procedures other than in-home vagus nerve stimulator therapy will take place at CHOA under the direct guidance of the PI. Parents will be trained on where to place electrodes, how to ensure that the electrodes make a good contact with the skin, and how to set the stimulation parameters. Patient is not required to have anyone sit with them during the stimulation procedure. At the end of two years, we will understand the benefits (or not) of nVNS in CIDP and the compliance of nVNS therapies in pediatric patients.

Specific Aim 1: Quantify functional changes in motor nerve conduction studies, hand held grip strength, and Rasch-built Overall Disability Scale (R-ODS) in CIDP patients receiving standard of care treatment and daily nVNS.

• **nVNS Therapy.** The nVNS therapy will be delivered using a handheld electrical neuromuscular stimulator

CHOA PI: [name] Study Protocol Version: 09/16/2021 (VitalStim 400) device. It is safe, effective at stimulating the vagus nerve, and easy to use by patients outside the clinic. Electrical neuromuscular stimulator devices have been used for years in pain-related preclinical and clinical research. Patients will be requested to deliver nVNS 2 times per day for 60 minutes each time for at least 5 days per week. The stimulation frequency (number of pulses) and amplitude (amount of current) will be set during the initial baseline session in the clinic and will be set to prevent discomfort to the patient or impact cardiorespiratory parameters. Initial stimulation parameters will be guided by previous reports of nVNS in patients. Patients will be trained on all appropriate methods for using the devices and asked to report the number of daily therapy sessions completed. Patients will be asked to continue their standard medication regimens which include in majority of cases 3 weekly IVIG (1 gm/kg) infusions, with or without steroids and plasma exchange.

- Handheld dynamometer: In the pediatric NM clinic we use a Jamar Handheld Dynamometer with reference range (in kilograms and pounds) for children ages 5-18 years. Both right and left hand grip strength would be measured. Best of the three attempts will be used in each hand. We routinely use dynamometer.
- **R-ODS:** Twenty four item motor scale based on day to day activities with a score of 0-48. The scale was designed for adult CIDP subjects however based on our experience in children the scale captures pediatric motor disability as well.
- NCS metrics: Motor nerve conduction studies are well tolerated in children. We routinely study median, ulnar, common fibular and tibial nerves on one side of the body. Distal and F wave latency, conduction velocity and amplitude will be recorded in all nerves. In addition, drop in motor amplitude and or temporal dispersion on proximal stimulation will be noted.

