#### **Hypotheses**

# We hypothesize that nVNS therapy can reduce systemic inflammation in CIPD patients, functionally halting degradation of motor nerve conduction and hand grip strength.

The specific aims of this proposal are to:

- 1. Quantify functional changes in motor nerve conduction studies, hand held grip strength, and Rash-built Overall Disability Scale (R-ODS) in CIDP patients receiving standard of care treatment and daily nVNS.
- 2. Characterize changes in serum cytokine profiles in patients receiving standard of care treatment and daily nVNS.

We anticipate observing a reduction in serum TNF- $\alpha$  levels after nVNS therapy, consistent with previously published clinical results. Serum cytokine levels will be statistically analyzed on a per patient basis, with each patient's baseline measurements used for comparison. will be used to determine statistically significant differences between subsequent serum cytokine profiles for the entire patient population and NCS metrics. Pearson's correlation coefficient will be used to understand the relationship between changes in serum cytokine levels and NCS metrics. Pearson's correlation coefficient will also be used to assess the relationship between number of therapy session (as reported by the patient) and serum cytokine levels.

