#### V. Inclusion and Exclusion Criteria

Inclusion criteria:

- 1. Diagnosis of CIDP based upon clinical/electrophysiological criteria
- 2. Patient should be on treatment for CIDP including IVIG and/ or steroids/ plasma exchange
- 3. 5-21 years of age

Exclusion criteria

- 1. Patients will be excluded from the study if they have inherited polyneuropathy, such as Charcot Tooth Marie disease.
- 2. Abnormal baseline EKG, heart disease, epilepsy, pregnancy, multiple sclerosis and diabetes mellitus.

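### F-wave latency is followed for 24 months in patients who may still be growing, with no height or limb-length correction, so it is biased towards apparent slowing at unchanged conduction velocity

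*Combined protocol and SAP*

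**What the plan says.** The nerve conduction paragraph under Specific Aim 1 names four motor nerves: "We routinely study median, ulnar, common fibular and tibial nerves on one side of the body". It then lists the measures: "Distal and F wave latency, conduction velocity and amplitude will be recorded in all nerves". Amplitude drop and temporal dispersion on proximal stimulation are also noted.

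Table 1 places these studies at baseline, 12 and 24 months. Its legend gives the comparison: "Baseline measurements before nVNS is added will be taken to determine change in physiological and functional outcomes over time". Section II sets the population: "A total of 15 subjects, from age 5 years to 21 years, will be included in the study". Section V repeats the age range.

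The hypothesis in Section I is that stimulation reduces inflammation, "functionally halting degradation of motor nerve conduction and hand grip strength". The analysis text there links nerve conduction metrics to a significance test and correlates them with cytokine changes by Pearson's coefficient. The name of the test is missing from the text as supplied, and I do not count that against the plan.

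No section mentions height, limb length, F-wave velocity, age- or height-based reference values for nerve conduction, or a growth covariate. A paediatric reference range is named for grip strength only. Section III says that sound natural history studies in paediatric CIDP are lacking.

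**The concern.** F-wave latency is the time for a signal to travel from the stimulation site to the spinal cord and back. It therefore depends on the length of the limb as well as on the nerve. A child who enters at 5 and is followed for two years will have longer limbs at the end. At unchanged velocity the latency rises, which is also the direction that slowing of conduction would produce.

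The hypothesis is that loss of motor conduction is halted. A measure that drifts towards apparent loss can hide a benefit or suggest harm. With a single arm and no usable historical comparator, nothing else in the design separates growth from disease. Growth also differs between patients in so wide an age range, which adds variation unrelated to the nerve to the correlations with cytokine change.

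**Working it through.** The plan gives no figure to reproduce: 15 patients are stated without an effect size, standard deviation or power. The check is geometric.

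**Inputs from the documents:** four nerves, two in the arm and two in the leg; studies at 0, 12 and 24 months; ages 5-21; n = 15; change from baseline; one arm.

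**Assumptions not in the documents:** growth over 24 months of 10-12 cm in young entrants and 0-3 cm near adulthood; path from stimulation site to cord of 0.40 of height (arm) or 0.65 of height (leg); velocity constant at 30-50 m/s; distal latency 4 ms and turnaround 1 ms, so about 5 ms that does not scale with height.

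**Formula.** F latency = distal latency + turnaround + 2D/v, where D is path length and v is velocity. At constant v, the change in F latency = 2 × (path fraction × growth) / v.

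**Absolute rise in young entrants**

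| | Lowest: 10 cm, 50 m/s | Highest: 12 cm, 30 m/s |
|---|---|---|
| Arm | 2 × 0.40 × 0.10 / 50 = 1.6 ms | 2 × 0.40 × 0.12 / 30 = 3.2 ms |
| Leg | 2 × 0.65 × 0.10 / 50 = 2.6 ms | 2 × 0.65 × 0.12 / 30 = 5.2 ms |

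**Relative rise.** Growth divided by height overstates this, because the 5 ms does not scale. Including it, for starting heights of 110-140 cm:

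- Smallest: arm, 140 cm, 10 cm growth, 50 m/s. Baseline = 2 × 0.56 / 50 + 5 ms = 27.4 ms; 1.6 / 27.4 = 5.8%.
- Largest: leg, 110 cm, 12 cm growth, 30 m/s. Baseline = 2 × 0.715 / 30 + 5 ms = 52.7 ms; 5.2 / 52.7 = 9.9%.
- Near-adult: leg, 165 cm, 3 cm growth, 30 m/s. Baseline = 2 × 1.0725 / 30 + 5 ms = 76.5 ms; 1.3 / 76.5 = 1.7%. With no growth the rise is zero.

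**Dependence on velocity.** For a 6 cm longer path, the rise is 6.0 ms at 20 m/s, 3.0 ms at 40 m/s and 2.0 ms at 60 m/s. The artefact is larger where conduction is slower, as in demyelination.

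**Effect of a correction.** F-wave velocity = 2D / (F − distal latency − turnaround). Take D growing from 0.80 to 0.86 m at 40 m/s. Raw latency goes from 5 + 40 = 45.0 ms to 5 + 43 = 48.0 ms (+6.7%). F-wave velocity is 1.60 m / 40 ms = 40.0 m/s before and 1.72 m / 43 ms = 40.0 m/s after.

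**Illustration of what a test would do.** Assume a paired t-test, n = 15, two-sided 0.05, and a rise of 2 ms from growth alone in each growing patient. The chance of a significant worsening at unchanged velocity (nominally 2.5% in that direction) is:

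| Patients growing | SD 2 ms | SD 3 ms | SD 4 ms |
|---|---|---|---|
| All | 95% | 67% | 44% |
| Two thirds | 59% | 33% | 22% |
| One third | 19% | 12% | 9% |

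The SD is that of the change not due to growth. Both it and the share still growing are assumed. The table shows only that the shift can matter, and how strongly that depends on the age mix.

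**The case against.** The strongest reply is that the plan only says latency will be recorded. It describes no specific analysis of F latency and nowhere says that a longer one counts as degradation. Uncorrected use is inferred from silence. That stands as a limit on the wording. However, the Table 1 legend applies change from baseline to physiological outcomes generally, and no correction appears anywhere.

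A reader might go further and infer that younger children will show degradation whatever the nerve does. The documents do not support that. The bias requires a patient who is still growing and a velocity that stays constant; a rise in a young child's velocity would offset part of it. Entry runs to 21, and the ages of the 15 patients are not known.

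A reader might also infer that the nerve conduction outcome as a whole is invalid. It is not. Conduction velocity is collected in the same nerves and is already distance-corrected. Distal latency would be affected only if its stimulation distance were not held fixed, which the plan does not say. No measure is named as decisive, so F latency may carry little weight.

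Nor do the documents show that growth biases the cytokine correlations. It would do so only if cytokine change also tracked age or growth; otherwise it mainly adds noise. Finally, the bias runs against the device, so through this measure growth cannot create a false benefit. That lowers the stakes, but a masked benefit or a false signal of harm is still a wrong answer.

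**Conclusion.** The point holds in a limited form and should be addressed. If the plan is followed as written, F-wave latency is biased towards apparent slowing in patients still growing, and the design cannot separate that from disease. The direction follows from geometry at constant velocity. The size, 1.6-3.2 ms (arm) and 2.6-5.2 ms (leg), or roughly 6-10% in young entrants and 0-2% in near-adults, rests on the growth, path and velocity assumptions above. How far it would affect the trial's conclusion cannot be determined, because neither the age mix nor the weight of F latency among the nerve conduction measures is given.

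**What to change.** Measure height, or limb path length, at each of the three nerve conduction visits. State in the analysis text that the F wave will be analysed as F-wave conduction velocity, or as latency adjusted for height at the same visit. Raw latency may still be reported but should not be interpreted alone as evidence of degradation. Use the corrected index in the correlations with cytokine change.

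The cost is one brief measurement at visits that already include a physical examination (baseline, 12 and 24 months in Table 1), and one line of analysis text. It should be settled before the first study: if height is not recorded at the time, the correction may not be recoverable later.

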# Specific Aim 2: Characterize serum cytokine profiles in CIDP patients receiving standard of care treatment and daily nVNS.

Stimulation of the vagus nerve has been shown to reduce pro-inflammatory cytokine levels in both animal and human investigations just after one session. In addition to evaluating functional changes in CIDP patients, we will quantify pro-inflammatory cytokine levels known to be elevated in CIDP patients. Serum cytokine assay available at Children's Healthcare of Atlanta laboratory will be used (https://www.testmenu.com/choa/Tests/671572). The assay contains 13 cytokines (interleukin 2, 4, 5, 6, 8, 10, 12, 13, 17, interleukin 1 beta, tumor necrosis factor alpha, interferon gamma, interleukin 2 receptor (SD25) soluble). Available normative laboratory values for above-mentioned cytokines will be compared with the CIDP subject values. Blood samples will be collected at baseline and each subsequent follow up visit as shown in Table 1 for profiling of serum cytokine levels. By correlating physiological (changes in cytokine levels) and functional effects (NCS, R-ODS, grip strength), we will develop a mechanistic basis for how and why nVNS benefits pediatric CIDP patients.

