#### III. Risks

Pediatric CIDP is a rare condition and disease course if often prolonged with relapse and remissions. The subject sample size is small and meaningful clinical/biochemical changes following an intervention in CIDP patient population takes months to years. In general, these limitations are true for the majority of rare pediatric neuromuscular conditions. Alternative approaches include comparing the study population with historical controls however well-done natural history studies in pediatric CIDP are missing. We also anticipate patient compliance challenges. The usage monitor on the nVNS device will allow us to account for that in the data analysis.

nVNS at the level of the neck in children has been used in multiple studies. Patients may experience irritation at the site of stimulation; however this typically subsides within 10-15 minutes post-stimulation. In addition, patients may experience soreness in the neck due to activation of muscles, which is expected to be temporary.

Rarely, EKG changes have been described with nVNS. The study design includes regular EKG checks and if any changes or abnormalities are noted, this will be deemed as serious adverse event (SAE) and lead to termination of device use in the study participants. A follow-up visit and EKG will be performed for these subjects and if EKG abnormalities persist, pediatric Cardiology evaluation will be requested.

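### Aim 2 promises a mechanism for nVNS benefit from a cytokine–function correlation that can arise, and reach significance, with no nVNS effect

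*Combined protocol and SAP*

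**What the plan says.** The closing sentence of Specific Aim 2 sets out the evidence and the conclusion. The evidence is a correlation: "By correlating physiological (changes in cytokine levels) and functional effects (NCS, R-ODS, grip strength"). The conclusion is that "we will develop a mechanistic basis for how and why nVNS benefits pediatric CIDP patients". The Hypotheses section names the statistic for the nerve conduction part: "Pearson's correlation coefficient will be used to understand the relationship between changes in serum cytokine levels and NCS metrics".

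The design around it is a single treated group. Section II states "A total of 15 subjects, from age 5 years to 21 years, will be included in the study", and the Table 1 text gives each child's own baseline as the comparator: "Baseline measurements before nVNS is added will be taken to determine change in physiological and functional outcomes over time". No sham or untreated group is planned. Specific Aim 1 has patients continue their usual IVIG, with or without steroids and plasma exchange.

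On the disease, Section III states "Pediatric CIDP is a rare condition and disease course if often prolonged with relapse and remissions", and Section I also describes a relapsing-remitting course. On the markers, Aim 2 states "we will quantify pro-inflammatory cytokine levels known to be elevated in CIDP patients". Section IV expects lower systemic inflammation to preserve conduction and improve function.

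**The concern.** To support a mechanism of nVNS, an analysis must contain some contrast in nVNS. This correlation contains none. It asks whether children whose cytokines fell more also improved more, and every one of those children was treated.

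The protocol's own premises supply another explanation. If CIDP raises these cytokines, and less inflammation means better function, then a child moving into remission tends to show lower cytokines and better function, and a child moving into relapse the reverse. A change in IVIG, steroids or plasma exchange could do the same. Either produces a correlation whatever nVNS does.

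If the plan is followed as written, such a correlation would be reported as the mechanism of an nVNS benefit in a rare paediatric disease for which, as Section III says, good natural history data are lacking.

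**Working it through.** The plan gives no alpha, power, effect size or expected correlation for this analysis, so there is no figure of its own to reproduce. The check asks how often the planned correlation would be significant if nVNS did nothing.

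**Inputs from the documents.** n = 15 (Section II). Cytokines, R-ODS, grip and nerve conduction are all measured at baseline and month 12 (Table 1). The statistic is Pearson's r on changes (Hypotheses).

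**Assumptions, not in the documents.** Two-sided alpha is 0.05. One fluctuating disease-activity factor A has 6-month autocorrelation ρ. At each visit the cytokine equals +λA plus noise and function equals −λA plus noise, each with unit variance; λ is the loading. There is no nVNS term.

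**Step 1: critical value.** With 13 degrees of freedom, t = 2.160, so |r| must exceed 2.160/√(13 + 2.160²) = 0.514.

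**Step 2: correlation implied with no nVNS effect.** Baseline to month 12 is two 6-month steps, so activity at the two visits correlates at ρ². The change in activity has variance 2(1 − ρ²), and the change in noise has variance 2(1 − λ²). Hence

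r = −λ²(1 − ρ²) / (1 − λ²ρ²).

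For λ = 0.7 and ρ = 0.3: −0.49 × 0.91 / (1 − 0.49 × 0.09) = −0.446/0.956 = −0.47.

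**Step 3: chance of significance for one cytokine–function pair** (simulation, 40,000 trials per row).

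| ρ | λ | implied r | significant |
|---|---|---|---|
| 0.3 | 0 | 0 | 5% |
| 0.3 | 0.3 | −0.08 | 6% |
| 0.3 | 0.5 | −0.23 | 13% |
| 0.3 | 0.7 | −0.47 | 44% |
| 0.3 | 0.8 | −0.62 | 74% |
| 0.8 | 0.7 | −0.26 | 15% |

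**Step 4: a different model.** Let each child be in relapse at each of two visits with probability p, with relapse shifting both measures by k within-visit standard deviations and no nVNS effect (100,000 trials per cell).

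| p | k = 1 | k = 2 | k = 3 |
|---|---|---|---|
| 0.1 | 6% | 17% | 40% |
| 0.3 | 9% | 42% | 82% |
| 0.5 | 11% | 51% | 89% |

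In this second model the test of mean cytokine change stays at about 5% throughout. The correlation can therefore be significant without any average change in cytokines.

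**The case against.** The best defence is that this is one aspirational sentence. The Aim 2 heading promises only to characterise cytokine profiles, the Table 1 text leaves open whether nVNS helps at all, and Section III concedes relapses and remissions, small numbers and the lack of usable historical controls. The plan also links exposure to biology: the Hypotheses section correlates reported sessions with cytokine levels, and Section III intends to use the device's usage monitor to account for compliance.

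This bears on how serious the point is but does not remove it. The concessions in Section III do not qualify the Aim 2 conclusion. The sessions analysis uses patient-reported, self-selected exposure, which disease activity may itself influence, and it is not tied to function. Table 1 collects concomitant medications, but no analysis uses them for this purpose.

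Two objections to the size also stand. No loading comes from the documents, and at weak loadings or with persistent disease activity the excess over 5% is small. The documents say that the cytokines are raised in CIDP; they do not say that they rise in relapse.

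A reader might infer that the real fault is a missing time order, because Aim 2 speaks of cytokine reduction after one session while Section III speaks of months to years. The documents do not support that reading: Section III puts biochemical as well as clinical change on the slow timescale. Nor would lagged change scores help. With no nVNS effect, ρ = 0.3 and loadings of 0.5 to 0.8, cytokine change from baseline to month 6 against nerve conduction change from baseline to month 12 shares the baseline visit, and gives mean r of −0.12 to −0.32 with about 7% to 23% significant. Cytokine change from baseline to month 6 against R-ODS or grip change from month 6 to month 12 shares month 6, and gives mean r of +0.06 to +0.19. The two are biased in opposite directions.

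**Conclusion.** The Aim 2 conclusion is wrong as written. In this single-group design a cytokine–function correlation describes association between inflammation and function in treated CIDP. It cannot separate nVNS from disease activity or background therapy.

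That conclusion rests on the design and needs no simulation. The size does: about 6% to 74% for one pair over loadings of 0.3 to 0.8 at autocorrelation 0.3, and lower with more persistent activity (at loading 0.7, 44% becomes 15% when the autocorrelation rises to 0.8). Loadings, autocorrelation and alpha are assumptions, and the link from relapse to cytokines is inferred from Specific Aim 2 and Section IV.

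A reader might go further and infer that a significant correlation is bound to appear. The documents do not support that; it can arise, with a probability they do not fix.

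**What to change.** Reword the last sentence of Specific Aim 2. It should say that the correlation is exploratory, that it describes the association between inflammation and function in treated CIDP, and that it is not evidence of how or why nVNS works.

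As a supporting analysis, report the correlation adjusted for changes in IVIG, steroids or plasma exchange, or separately by whether they changed, using the concomitant medication records in Table 1. With 15 children this will be imprecise, and it does not turn the correlation into evidence about nVNS.

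Do not add lagged change-score tests, or a rule for calling a result consistent with an nVNS mechanism. The lagged scores share a visit and are biased with no nVNS effect, and nVNS use is self-selected.

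The cost is a change of wording and one extra analysis of data already scheduled, with no added visits, samples or patients. The downside is a more modest Aim 2 claim.
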